#### 2.6.2.2 From the Investigational brochure April 30, 2012:

Since approval, AMAG has conducted one clinical trial (Protocol Number FER-CKD-201). This was a randomized, open-label trial that compared the safety and efficacy of ferumoxytol to iron sucrose for the treatment of IDA in CKD subjects either on or not on dialysis. In this trial, 162 patients were randomized in a 1:1 ratio to either ferumoxytol or iron sucrose. Ferumoxytol was administered as a 1.02 g course given as a regimen of 2 x 510 mg within 2 to 8 (5±3) days. Related AEs experienced by ferumoxytol-treated subjects included one of each of the following (1.3%): anaphylactic reaction, dysgeusia, feeling hot, flushing, headache, injection site hematoma, injection site pain, and nausea.

There was 1 SAE considered related to ferumoxytol treatment. The subject experienced an anaphylactic reaction, described as a systemic allergic reaction, after receiving the first dose, and was treated with epinephrine, Benadryl, Solu-Cortef and IV normal saline on the day of the event. The event was subsequently resolved the same day.

#### 2.6.3 Post-Marketing Program

In March of 2015 the FDA placed a black box warning on ferumoxytol stating:

#### WARNING: RISK FOR SERIOUS HYPERSENSITIVITY/ANAPHYLAXIS REACTIONS

Fatal and serious hypersensitivity reactions including anaphylaxis have occurred in patients receiving Feraheme. Initial symptoms may include hypotension, syncope, unresponsiveness, cardiac/cardiorespiratory arrest.

- Only administer Feraheme when personnel and therapies are immediately available for the treatment of anaphylaxis and other hypersensitivity reactions.

- Observe for signs or symptoms of hypersensitivity reactions during and for at least 30 minutes following Feraheme infusion including monitoring of blood pressure and pulse during and after Feraheme administration.
- Hypersensitivity reactions have occurred in patients in whom a previous Feraheme dose was tolerated.

In the black box warning the FDA updated their recommendations of how ferumoxytol should be given. The option to give ferumoxytol (510mg) as a fast undiluted injection in approximately 1 minute has been removed. It was recommended that ferumoxytol (510mg) be given over at least 15 minutes. To accommodate for this, the dose of ferumoxytol will be given in three separate, fractionated doses. The rate of administration of the second and third doses will be slowed down to no faster than 1 mL/s.

Based on communication with AMAG Pharmaceuticals, manufacturer of ferumoxytol, all recommendations apply to iron replacement therapy where infusion rate and dilution do not impact efficacy. However, for an imaging indication certain infusion parameters are required to gain information, such as dynamic imaging. Increased infusion rate will only affect the first injection of 1 mg/kg, which is a small fraction of the full therapeutic dose, and therefore may minimally increase the risk of adverse reactions. The next two injections are given at a slower rate. The recommended 15 minutes has no scientific basis, it has been chosen arbitrarily. For MR imaging stopping the scanner for 15 minutes would be disadvantageous. Applying multiple injections, which is not the case with iron replacement therapy, may increase safety, compared to continuous injection. This may contribute to the fact that in our patient population only minor adverse reactions have been reported.

## 2.6.4 OHSU Toxicity Data

As of April 1, 2015, a total of 621 infusions of ferumoxytol had been completed on 287 study subjects as part of OHSU's Blood Brain Barrier sponsored IRB approved protocols. The dose has ranged from 75 to 510 mg of ferumoxytol (0.5 to 11 mg/kg). Toxicities for this group as of April 1, 2015 show no grade 4 or 5 toxicities (CTCAE version 3) that were attributed to ferumoxytol. Two incidents of grade 3 toxicities were possibly attributable to ferumoxytol (one incident of constipation and one of neck pain). The most common adverse events associated with ferumoxytol were 20 (3% of total infusions) incidents of mild, transient hypertension and 5 (0.8% of total infusions) incidents of diarrhea. There have been no incidents of hypotension, syncope, unresponsiveness or cardiorespiratory arrest with these 621 administrations of ferumoxytol.

## 3 SUBJECT SELECTION

### 3.1 Eligibility Criteria

- 1) Subjects with radiographically suspected, histologically or cytologically confirmed primary brain tumors or brain metastasis are eligible.
- 2) Subjects may be enrolled at any point in diagnosis or treatment.
- 3) Subjects must have had radiographically evaluable or measurable disease with standard MR imaging.
- 4) .
- 5) Age  $\geq$ 18 years. Both men and women and members of all races and ethnic groups will be included.
- 6) ECOG performance status  $\leq$  3 (KPS  $\geq$  30).

- 7) Ability to understand and the willingness to sign a written informed consent document, or have a representative able to consent for the subject.
- 8) Sexually active women of child-bearing potential and men must agree to use adequate contraception (hormonal or barrier method of birth control; or abstinence) prior to study treatment and for the duration of study treatment. Should a female become pregnant or suspect she is pregnant while participating in this study, she should inform her treating physician immediately.
- 9) Subject agrees to complete follow up visit.

### **3.2 Exclusion Criteria**

- 1) Subjects with clinically significant signs of uncal herniation, such as acute pupillary enlargement, rapidly developing motor changes (over hours), or rapidly decreasing level of consciousness.
- 2) Subjects who have a contraindication for MRI: metal in their bodies (a cardiac pacemaker or other incompatible device), are severely agitated, need monitored anesthesia for scanning, or have an allergy to Gd contrast material.
- 3) Subjects with known hepatic insufficiency or cirrhosis
- 4) History of allergic reactions attributed to compounds of similar chemical or biologic composition to ferumoxytol
- 5) Subjects with known or suspected iron overload (genetic hemochromatosis or history of multiple transfusions)
- 6) Subjects expecting to undergo surgery between the imaging sessions. Subjects may undergo surgery at any time before the first, or after the last imaging session. This exclusion only applies to each study visit (3 day scanning session), and does not apply to the time (at least 3 weeks) between each study visit.
- 7) Uncontrolled concurrent illness including, but not limited to, ongoing or active infection, symptomatic congestive heart failure, unstable angina pectoris, cardiac arrhythmia, or psychiatric illness/social situations that would limit compliance with study requirements.
- 8) Pregnant or lactating women are excluded from this study because of possible risk to the fetus or infant.
- 9) Inability or unwillingness to undergo the complete series of imaging sessions. Inability or unwillingness to complete the one month follow-up.
- 10) HIV-positive subjects on combination antiretroviral therapy are ineligible because of the potential for pharmacokinetic interactions with ferumoxytol.
- 11) Subjects with GFR < 50.
- 12) Subjects with three or more drug allergies from separate drug classes.

## **4 CONTRAST AGENT FORMULATION AND PROCUREMENT**

### **4.1 Gadolinium**

Gadolinium is a standard contrast agent used in clinical practice and will be administered on day 1 as an I.V. bolus of 0.1 mmol/kg at a flow rate of up to 3 mL/s, followed by a saline flush. for dynamic MR imaging followed by routine MR imaging. The appropriate

volumes of contrast agents are based on the patient's weight (0.2 ml/kg gadoteridol + 20ml saline flush).

#### **4.2 Ferumoxytol**

- 4.2.1 **Agent Accountability:** The Investigator, or a responsible party designated by the Investigator, must maintain a careful record of the inventory and disposition of the study agent.
- 4.2.2 **Availability:** Ferumoxytol is purchased by the investigators from the manufacturer, AMAG Pharmaceuticals, Inc. (Cambridge, MA)
- 4.2.3 **Product description:** Ferumoxytol is a semi synthetic carbohydrate coated ultrasmall superparamagnetic iron oxide particle. The drug is formulated with mannitol; each vial contains 30 mg/mL of iron and 44 mg/mL of mannitol. A dose of 510 mg of iron is 17 mL. Ferumoxytol is isotonic: the osmolality is 270-330 mOsm. The amount of free (BDI) iron for ferumoxytol is approximately six - fold lower than for currently approved parenteral iron products at a similar dose. The product contains no preservatives. The pH is 6 to 9.
- 4.2.4 **Preparation:** The appropriate volume of drug is based on the subject's weight. The drug will be stored at room temperature (68-77 degree Fahrenheit) away from direct sunlight. The solution will be prepared and dispensed by the investigational drug pharmacist. The Ferumoxytol will be injected in the MR suite by either a nurse or technician.

The ferumoxytol will be diluted 1:1 to make a 15mg/ml solution. The total dose of ferumoxytol will be 4 mg/kg (to a maximum of 510 mg), and will be administered intravenously on day 2.

The dilution and injection parameters may be adjusted to obtain optimal signal changes. The total dose will not exceed 4 mg/kg or 510 mg.

See Section 5.3.4 for administration.

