**5.3.4 Day 2**

Imaging

- Anatomical imaging on 3T & 7T and dynamic MRI (with ferumoxytol, see section 4.2). A subset of 25 of the 150 subjects will only undergo MRIs on the 7T magnet.
- Dynamic imaging will be performed on the same scanner as on which the dynamic the dynamic imaging was acquired on Day 1(as described below on Section: 6.0). Ferumoxytol Administration:
  - The ferumoxytol will be diluted 1:2 to make a 10mg/ml solution. The dose of ferumoxytol will be 4 mg/kg (to a maximum of 510 mg), and will be administered intravenously on day 2.
  - Dose 1: Give 1/4th of the total dose (1mg/kg); inject at up to 3 ml/sec followed by a saline flush. This rate is required for adequate signal change during the dynamic imaging.
  - Dose 2: Give 3/4th of the total dose (3mg/kg); inject no faster than 1 ml/sec and followed by a saline flush
  - 
  - The dilution and injection parameters of the ferumoxytol may be adjusted to obtain optimal signal changes on MRI/MRA and to decrease the possibility of an allergic reaction. Injection rate can be varied based on the participant's IV site, but the total dose will never exceed 510mg.

Monitoring

- A clinical examination will be performed before and after the MRI session on Day 2.. Blood pressure and pulse will be monitored before the first dose of ferumoxytol and after each dose of ferumoxytol, and at 30 minutes after the initial dose of ferumoxytol.

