## **Day 2**

1. Standard MRI sequences: axial T1, (MPRAGE, T2, T2\*, PD, DWI images will be acquired only when quality of images are not good or if they were not acquired for some reason in first session)
2. TOF angiography (only when quality of image is not good or was not acquired for some reason on first session)
3. Quantitative T1 images
4. DSC MR (T2\* weighted) for perfusion with ferumoxytol bolus (maximum dose: 1mg Fe/kg) the remaining 3mg/kg to be administered after this series)
5. Quantitative T1 images for permeability measurement will be performed 4 times
6. TOF angiography (post ferumoxytol)
7. Standard MRI sequences (post contrast): MPRAGE, axial T1, T2, T2\* weighted images.

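### The Day 2 ferumoxytol dilution is stated two ways, and the only clock-timed BP and pulse check runs from the first injection, not the last (minor)

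*Combined protocol and SAP*

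**What the plan says.** **Dilution.** Section 4.2.4 (Preparation) gives "The ferumoxytol will be diluted 1:1 to make a 15mg/ml solution" and assigns the task: "The solution will be prepared and dispensed by the investigational drug pharmacist". A nurse or technician injects. Section 5.3.4 (Day 2), to which 4.2.4 refers for administration, gives "The ferumoxytol will be diluted 1:2 to make a 10mg/ml solution". Both sections describe 4 mg/kg up to 510 mg on Day 2, and both allow the dilution and injection parameters to be adjusted. Section 5.3.4 splits the dose into a quarter (1 mg/kg, up to 3 ml/s) and three quarters (3 mg/kg, at most 1 ml/s). Section 6.1 places the second part after the DSC series: "the remaining 3mg/kg to be administered after this series". It gives no clock time.

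**Monitoring.** Section 5.3.4 requires: "Blood pressure and pulse will be monitored before the first dose of ferumoxytol and after each dose of ferumoxytol", then one further reading, "and at 30 minutes after the initial dose of ferumoxytol". It also states: "A clinical examination will be performed before and after the MRI session on Day 2". The boxed warning reproduced in section 2.6.3 asks for observation during and "for at least 30 minutes following Feraheme infusion including monitoring of blood pressure and pulse during and after Feraheme administration".

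**The concern.** The two dilution statements are both defaults for the same preparation, and they disagree. The adjustment clauses allow departures from a default but do not say which default applies. The cross-reference in 4.2.4 covers administration, whereas the pharmacist's task is described in 4.2.4 itself. Staff who prepare and staff who inject could therefore work from different figures. Because the injection limits are in ml/s, the concentration also sets how fast iron enters the vein.

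The timed BP and pulse reading is counted from the injection that carries a quarter of the iron. The other three quarters come later, and no reading or minimum observation time is counted from that point. Section 2.6.3 argues openly for departing from the 15-minute infusion time. It offers no argument for a shorter observation period, so the choice of starting point does not read as a reasoned deviation. At stake is a clear instruction on a drug whose label warns of fatal hypersensitivity, in a study where a visit may be repeated up to four times.

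**Working it through.** **Inputs.** Vial 30 mg/mL (4.2.3). Dose, split and rate limits from 5.3.4. DSC timing from 6.3: 45 volumes at 2.0 s (3T) and 90 volumes at 1.5 s (7T). Listed 3T scan times are 3 minutes for the PWI entry and 6 minutes for the T2*-weighted entry. Body weight of 70 kg is assumed; the cap is reached at 510/4 = 127.5 kg.

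**1. The plan's own figures.** Concentration = 30/(1 + parts diluent). For 1:1, 30/2 = 15 mg/ml; for 1:2, 30/3 = 10 mg/ml. Each section agrees with itself, so neither figure is a single-digit slip.

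**2. What is the same.** Drug volume from the vial at 70 kg: 280/30 = 9.3 ml under either text; at the cap, 510/30 = 17 ml. A quarter of the dispensed volume is 1 mg/kg at either strength.

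**3. What differs.**

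| | 15 mg/ml | 10 mg/ml |
|---|---|---|
| Diluted volume, 70 kg | 280/15 = 18.7 ml | 280/10 = 28.0 ml |
| Diluted volume, cap | 510/15 = 34 ml | 510/10 = 51 ml |
| Iron rate, dose 1 at 3 ml/s | 45 mg/s | 30 mg/s |
| Iron rate, dose 2 at 1 ml/s | 15 mg/s | 10 mg/s |
| Dose 1 duration, 70 kg | 4.67/3 = 1.56 s | 7.0/3 = 2.33 s |
| Dose 1 duration, cap | 8.5/3 = 2.83 s | 12.75/3 = 4.25 s |

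The iron rates differ by 45/30 = 15/10 = 1.5. The bolus durations differ by 0.78 s (70 kg) and 1.42 s (cap). Both are below one DSC frame, which is 2.0 s at 3T and 1.5 s at 7T.

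**4. Timing of the 30-minute reading.** Take dose 1 at the start of DSC and dose 2 directly after it at 1 ml/s. Dose 2 then takes 210/15 = 14 s to 210/10 = 21 s at 70 kg, and 382.5/15 = 25.5 s to 382.5/10 = 38.25 s at the cap.

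- Earliest end of dose 2: 45 × 2.0 + 14 = 104 s = 1.7 min. The reading comes 30 − 1.7 = 28.3 min after the last injection.
- DSC of 3 minutes, cap, 10 mg/ml: 180 + 38.25 = 218.25 s = 3.6 min. The reading comes at 26.4 min.
- DSC of 6 minutes, cap, 10 mg/ml: 360 + 38.25 = 398.25 s = 6.6 min. The reading comes at 23.4 min.

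The 7T series (90 × 1.5 = 135 s) lies inside this range. The shortfall is thus about 2 to 4 minutes, or up to about 7 with the longer listed scan. A later or slower dose 2 widens it.

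**5. Time in the scanner after dose 2.** The listed 3T times for the sequences that 6.1 places after dose 2 are: quantitative T1 4 × 5, TOF 5, MPRAGE 7, axial T1 4 and T2 2, a total of 38 min with T2* not counted. If the 45 minutes in 7.3 run from dose 1, the T1 series alone ends 45 − 6.6 = 38.4 to 45 − 1.7 = 43.3 min after dose 2. A subject who completes the session therefore passes 30 minutes while still being imaged.

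**The case against.** The case for leaving this alone is that nothing much follows from it. The dose is fixed in mg/kg under the same cap, the pharmacist dispenses it, and 5.3.4 divides it by fraction, so either strength gives the right amount of iron. BP and pulse are also taken, untimed, after each dose, including the last. An examination closes the session, 5.4 lists symptoms to watch for during infusion, and 2.6.4 reports no hypotension in 621 local infusions. As quoted, the warning asks for 30 minutes of observation with BP and pulse monitored during and after administration; it does not demand a reading at or beyond 30 minutes. Someone who stops before dose 2 still has a full 30 minutes after the only injection received. Section 5.6 mainly concerns scanner availability and crossover, so it is weak evidence that people will stop after dosing.

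All of this stands, and it is why the point is minor. It does not say which dilution is intended, and it does not supply an observation time counted from the last injection.

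A reader might infer more, in three ways:

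- **A dosing error is built in.** It is not. Dose 1 would become 7.0 × 15/70 = 1.5 mg/kg, or 4.67 × 10/70 = 0.67 mg/kg, only if a volume worked out from one section were drawn from a solution made to the other. The plan does not instruct that, and a labelled syringe should prevent it.
- **The perfusion comparison in Aim 2 is biased.** The documents do not show this; the difference in bolus duration is below one frame.
- **Subjects go unobserved after the larger injection.** They do not; step 5 of the working and the checks after each dose show otherwise for anyone who completes the session.

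**Conclusion.** Both points hold and both are minor. The default dilutions in 4.2.4 and 5.3.4 conflict. The consequence is a diluted volume and an iron delivery rate that differ by a factor of 1.5, with no change in the intended dose and a negligible effect on imaging.

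The timed check starts from the wrong injection. Its shortfall assumes that dose 2 directly follows DSC and is given at its maximum rate. The upper figure of about 7 minutes also needs the 6-minute listed scan and a subject at the dose cap, at least 127.5 kg. In practice the gap is one timed reading, plus the few subjects who might stop soon after dose 2, for whom no minimum observation is stated. No estimate or conclusion of the study changes.

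**What to change.** 1. State one default dilution in both 4.2.4 and 5.3.4. The investigators must choose it, since the documents do not show which is intended. The adjustment clauses can stay.
2. In 5.3.4, time the 30-minute BP and pulse check, and a minimum 30-minute observation, from the end of the last ferumoxytol injection given. Apply this also to subjects who stop imaging early, and keep the checks before dose 1 and after each dose. Wording tied to the last injection given also works whatever the number of injections: 2.6.3 speaks of three, while 5.3.4 lists two.

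The cost is a short amendment to two sections. For subjects who complete the session, one reading moves by about 2 to 7 minutes, or more if dose 2 is delayed. For those who stop soon after dose 2, the observation time is extended by a similar amount.

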#### **4.3 Expected adverse events**

As described in the Investigator's Drug Brochure for ferumoxytol, a total of 1740 subjects (patients and healthy volunteers) were given one or more doses of ferumoxytol. Safety was determined in subjects through an analysis of changes in pre and post-dose blood chemistry, urinalysis, vital signs, results of physical examinations, electrocardiograms (ECG), and by the incidence of adverse events. There were no clinically significant changes noted by the investigators in ECG, vital signs, or clinical chemistries. There have been three serious adverse events considered related or possibly related to ferumoxytol. Two cases of peritonitis in patients undergoing continuous ambulatory peritoneal dialysis, occurring 13 and 30 days after administration of ferumoxytol were considered 'possibly related'. Both patients had prior histories of peritonitis. One patient with a history of allergies had an anaphylactic reaction that was considered 'related' to ferumoxytol.

On June 20, 2009, the FDA approved ferumoxytol (Feraheme™) to treat iron deficiency anemia and adult chronic kidney disease patients. The recommended dose is an initial 510 mg IV injection followed by a second 510 mg IV injection three to eight days later. Ferumoxytol is now commercially available in the U.S.A.

#### **4.4 Safety**

The ferumoxytol clinical development program has been comprised of eleven studies. These included three Phase 1 studies (two dose-escalation studies and a study of the

electrocardiographic/QTC effects of ferumoxytol), two Phase 2 studies that evaluated the safety and efficacy of ferumoxytol for iron replacement in patients with CKD, and two Phase 2 imaging studies that assessed the feasibility of ferumoxytol as an MRI contrast agent. There were three open-label Phase 3 studies that examined the efficacy and safety of ferumoxytol relative to oral iron in patients with Chronic Kidney Disease (CKD) Stages 1-5 either on or not on dialysis. A fourth Phase 3 study in patients with any stage of CKD evaluated the safety of ferumoxytol relative to placebo in a cross-over, double-blind manner. Ferumoxytol has been evaluated at exposures up to 2 x 510 mg, including two courses of 2 x 510 mg in three of the four Phase 3 studies. Specifically, the following regimens of ferumoxytol were given during the clinical program:

- ≤4 mg Fe/kg
- 1 x 125 mg
- 1 x 250 mg
- 1 x 510 mg
- 8 x 128 mg
- x 255 mg
- x 510 mg

Approximately 1,740 patients have been exposed to ferumoxytol in the entire clinical program, and approximately 1,509 patients have been exposed to ferumoxytol in the Phase 3 studies. To date, only one patient (0.06% of all patients exposed to ferumoxytol) has experienced an anaphylacoid reaction following treatment with ferumoxytol; this patient had a history of multiple drug allergies and experienced an anaphylactoid reaction (hot flashes and itching, with no respiratory compromise) and severe hypotension a few minutes after receiving ferumoxytol. There have been no deaths that were considered to be related to ferumoxytol treatment. There were 28 deaths in the clinical program, all of which have occurred in Phase 3 studies, with 16 deaths among the 1,740 patients exposed to ferumoxytol (0.9%) and 8 deaths among the 296 patients exposed to oral iron (2.7%). Four deaths occurred in patients who had signed an informed consent for enrollment but did not receive any test article. All deaths in the clinical program have been in patients with CKD, who have a high risk of death due to cardiovascular disease and other causes. In completed studies that used oral iron as a comparator, there was a lower rate of SAEs among patients exposed to ferumoxytol than among patients exposed to oral iron: 4.4% of ferumoxytol-treated patients (64 of 1,451 patients) vs. 10.7% of oral iron-treated patients (17 of 159 patients). Patients exposed to placebo had the lowest rate of SAEs (1.7%; 13 of 780 patients). One patient each following ferumoxytol (0.1%), oral iron (0.6%), and placebo (0.1%) experienced an SAE that was considered by the investigator to be related to treatment. In Phase 3 Study 62,745-5, which enrolled CKD patients undergoing hemodialysis, 31 of 199 (15.6%) patients experienced an SAE following ferumoxytol administration and 8 of 70 (11.4%) patients experienced an SAE following oral iron administration. These data were taken from an unlocked database and therefore are preliminary and patient to final verification. In the Phase 3 studies in patients with CKD (62,745-5, 62,745-6, 62,745-7, and 62,745-8, in which approximately 1,509 patients were exposed to ferumoxytol), the most common adverse events following ferumoxytol administration included nausea, diarrhea, dizziness, headache, and peripheral edema. These adverse events were usually more common in the oral iron group than the ferumoxytol group (in Studies 62,745-5, 62,745-6, and 62,745-7, which utilized oral iron as a comparator). Hypotension was one of the more common adverse events in Study 62,745-7 and occurred more frequently in the ferumoxytol group (5.0%) than the oral iron group (1.4%). By contrast, preliminary data show that there have been

lower rates of hypotension in Study 62,745-5 (1.8%, 1.7%, and 0% in the ferumoxytol 2x510 mg, ferumoxytol 4x255 mg, and oral iron groups, respectively); hypotension rates were similar between the ferumoxytol and placebo groups (1.3% vs. 0.8%) in the large safety study, Study 62,745-8; and there were no hypotension adverse events in Study 62,745-6.

An independent Data Monitoring Committee met to review the clinical safety data for all Phase 3 studies in October 2005, February 2006, June 2006, October 2006, and March 2007, and they identified no safety concerns.

